**9.1.4 Plan to maximize subject retention and minimize loss of data**

Significant efforts will be made to maintain maximum subject retention and follow up data and minimize the percentage of missing data.

[REDACTED]

[REDACTED]

[REDACTED]

[REDACTED]

[REDACTED]

### 9.1.5 Imputation of missing diary data during the home trial will be performed conservatively

Data missing from any day of diary during the first 4 weeks of the home trial will be imputed from baseline diary data, using the average pain score from the baseline week. Scores will only be imputed if recall data are unavailable and cannot be obtained.

[REDACTED]

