### 9.3 Secondary clinical efficacy endpoint analysis

Additional endpoints below will be assessed to document further the effectiveness of using the SPRINT Peripheral Nerve Stimulation (PNS) System for the symptomatic relief and management of post-amputation pain.

- Durability of the treatment effect on average pain intensity (Primary Endpoint) after 8-week home trial

The durability of the treatment effect on average pain intensity compares the proportion of subjects who successfully achieve  $\geq 50\%$  reduction from baseline in Group #1 at end of 8-week home trial relative to that in Group #2 at end of 4-week sham period, examining the statistical superiority of the proportion of successes of Group #1 over the proportion of successes of Group #2. The post-amputation pain intensity scores will be determined for each subject by applying the same method used for the primary endpoint: taking the mean of the daily average pain intensity (BPI-SF Question #5) reported in the 7-day diary at baseline compared to the mean score for the same region(s) of pain reported over the 8 weeks of treatment (*i.e.*, the average of all scores in the diaries during this period) for Group #1. To be

considered a success, subjects must have  $\geq 50\%$  reduction in all qualifying regions of pain, defined as regions of RLP and PLP with a baseline pain score  $\geq 4$  that received blinded treatment. The proportion of successes in Group #1 will be compared to the proportion of successes in Group #2 during the sham stimulation phase (Weeks 1-4 of the home trial). The null hypothesis is that there is no difference in success rates between the two treatment groups, versus the alternative hypothesis, that the success rates differ from one another.

- Durability of the treatment effect on average pain intensity (Primary Endpoint) at monthly intervals after start of therapy (3 - 12 months after start)

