### 9.5 Per Protocol and Intent to Treat Analyses

Analyses of the primary and secondary effectiveness endpoints will be conducted on the intent-to-treat (ITT) population and the per-protocol (PP) population at each specified study interval defined as follows:

PP Population: The per-protocol population will consist of all randomized subjects who meet the following criteria:

- Were implanted [REDACTED]
- For Group #1 subjects: paresthesia coverage in the target areas.
- Have an adequate number of average pain intensity (BPI-5) scores in the diaries during the primary endpoint period (*i.e.*, first 4 weeks of home trial). These diaries must not be missing more than 50% of the pain scores to be included in the PP population.

[REDACTED]

- Continued study eligibility (subjects cannot have a change in medical status that would have otherwise excluded them from the study)

ITT Population: The intent-to-treat population will include all randomized patients who were implanted [REDACTED] that is, patients will be analyzed according to the treatment group to which they were randomized. Evaluable subjects are defined as those who were randomized and implanted with a lead.

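### On the visible text, the diary fill and the per-protocol diary check stop at week 4, while the secondary 8-week durability score for Group #1 runs to week 8

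*Combined protocol and SAP*

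**What the plan says.** All references are to the combined protocol and SAP.

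- **9.1.5, heading:** "Imputation of missing diary data during the home trial will be performed conservatively". Section 9.3 describes the home trial as lasting 8 weeks.
- **9.1.5, rule:** "Data missing from any day of diary during the first 4 weeks of the home trial will be imputed from baseline diary data", at the baseline-week average. A condition follows: "Scores will only be imputed if recall data are unavailable and cannot be obtained". A redacted block comes next.
- **9.3, durability after the 8-week home trial:** the score is found by "applying the same method used for the primary endpoint". For Group #1 this is spelled out as the baseline diary mean against the mean over 8 weeks of treatment, that is, "the average of all scores in the diaries during this period". Success needs at least a 50% reduction in every qualifying region. The comparator is Group #2 in its sham phase, weeks 1-4.
- **9.1, scoring of the primary endpoint:** for each leg with leads, only days with every lead in position count. The example given is late placement in a second leg.
- **9.5:** primary and secondary effectiveness endpoints are analysed in both the ITT and PP populations. One PP criterion is "Have an adequate number of average pain intensity (BPI-5) scores in the diaries during the primary endpoint period", which 9.5 defines as the first 4 weeks, with no more than half the scores missing. The visible ITT definition (randomized and implanted) has no diary requirement.

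**The concern.** A durability endpoint should register loss of effect after week 4. On the visible text, the two safeguards against missing diaries both end at week 4, and the score then rests on whatever diaries exist. A Group #1 subject who stops keeping diaries at day 28 would carry the weeks 1-4 result forward as the 8-week result, and could do so in both populations.

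The comparison is also uneven. Group #2's whole window lies where unrecoverable days are set to baseline, whereas half of Group #1's window lies outside it. The difference favours Group #1 in a comparison meant to show Group #1 superior. What is at stake is the credibility of one secondary claim, that the effect holds through 8 weeks.

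**Working it through.** **No plan figure to reproduce.** The plan prints no figure for this endpoint. Its power statement in 9.1.2 concerns the primary endpoint, and the expected proportions are redacted.

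**Inputs.** Home trial 8 weeks = 56 days (9.3); visible fill window 4 weeks = 28 days (9.1.5); success threshold 50% (9.3); diary check at most 50% missing over 4 weeks (9.5); up to 27 per group (6.2).

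**Step 1: the score under two readings.** Let a Group #1 subject record diaries on days 1 to d with mean relief r, and nothing afterwards, with no recall data.

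- Available days only: 8-week relief = r.
- Baseline fill to day 56: a filled day has 0% relief, so 8-week relief = r × d/56. Success needs r ≥ 50 × 56/d.

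| Last recorded day d | r needed, available days | r needed, fill to day 56 | Score after fill if r = 60% |
|---|---|---|---|
| 28 | 50% | 100% | 30% |
| 35 | 50% | 80% | 37.5% |
| 42 | 50% | 66.7% | 45% |
| 49 | 50% | 57.1% | 52.5% |
| 56 | 50% | 50% | 60% |

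A subject with 60% relief who stops at day 28, 35 or 42 succeeds on available days and fails after the fill. One who stops at day 49 succeeds either way.

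**Step 2: stopping against staying.** A subject with 60% relief in weeks 1-4 who keeps the diary and records 20% in weeks 5-8 scores (60 × 28 + 20 × 28)/56 = 40% and fails. The same subject with no diaries after day 28 scores 60% and succeeds. To stay a success with full diaries, weeks 5-8 must average at least 100 − 60 = 40%.

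**Step 3: the PP check.** The minimum is 50% of 28 = 14 days, and 14/56 = 25% of the durability window. This bears on PP membership (the other PP criteria still apply) rather than on success. If the other 14 days in weeks 1-4 are filled at baseline, the subject needs r × 14/28 ≥ 50%, that is, r = 100%. The likelier problem case has full diaries to day 28 and none after.

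**Step 4: early lead removal.** If the leads-in-place limit in 9.1 is carried into weeks 5-8 with the rest of the primary method, days after early removal drop out of the average. The result is the available-days column above, whatever 9.1.5 says.

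**Step 5: weight of one subject.** 1/27 = 3.7 percentage points; it is larger if fewer than 27 are enrolled. The documents give no dropout or success rates, so the counts below are assumptions, as is the two-sided Fisher test.

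| Assumed successes, Group #1 vs Group #2 (of 27 each) | p | One Group #1 success lost | Two lost |
|---|---|---|---|
| 12 vs 3 | 0.014 | 0.028 | 0.054 |
| 14 vs 5 | 0.021 | 0.042 | 0.077 |
| 16 vs 5 | 0.005 | 0.010 | 0.021 |

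Two subjects can matter when the result is close and do not when it is clear.

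**The case against.** The strongest reply is that the missing rule may be in the document but blacked out. The heading of 9.1.5 reaches across the whole home trial, and a redacted block follows the four-week rule, just where a weeks 5-8 rule would sit. Section 7.6 on early termination, much of 9.1.4 and part of the PP list in 9.5 are also redacted. In addition, 9.3 invokes the primary method, which can be read as bringing the fill with it. This stands: a reader might infer that such a subject is definitely scored on early days alone, and the documents do not establish that. It does not settle the point. The wording that follows the cross-reference in 9.3 describes averaging and not imputation, and carrying the primary method over also brings the leads-in-place limit. The printed PP window is explicitly four weeks.

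A reader might also infer that every missing day in Group #2's window is set to zero relief. It is not: recall data come first, the leads-in-place limit applies there too, and Group #1 has the same treatment in weeks 1-4. Any imbalance is confined to weeks 5-8.

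Finally, baseline fill is severe, since a subject stopping at day 28 would need 100% relief. That is fair. The case for it is consistency: it is the plan's own choice for weeks 1-4 and for all of the comparator's window.

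**Conclusion.** The point holds as a mismatch of windows on the visible text. The 8-week endpoint is scored over 56 days, but the printed fill and the printed PP check cover 28. If no redacted rule applies and the fill is not carried forward, a Group #1 subject with at least 50% relief in weeks 1-4 and no later diaries is an 8-week success, and the diary check can be met with a quarter of the window recorded. Each such subject adds 3.7 points to the Group #1 rate at 27 per group. How many there would be is unknown, so the overall effect cannot be sized from the documents.

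Two wider conclusions are tempting but unsupported. The diary gap gives no ground for a missing-equals-failure rule at the month 3-12 assessments, which use recall scores rather than home-trial diaries, nor for counting every withdrawal as a failure. It also does not touch the primary endpoint, whose four-week window matches both printed rules.

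**What to change.** 1. In 9.1.5 and 9.3, state, or confirm if it is already in redacted text, that for the 8-week durability endpoint diary days missing in weeks 5-8 in Group #1 are handled as in weeks 1-4: recall data first, then the baseline-week average.
2. In the same place, say how the leads-in-place limit of 9.1 applies to days after early lead removal or withdrawal, and which provision governs when that limit and the fill conflict. Without this, the first change could be bypassed for subjects whose leads come out early.
3. In 9.5, tie the 50% diary check to the window of the endpoint being analysed. Here that is weeks 1-8, so at least 28 of 56 days for Group #1.

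These are wording changes that need no new data. The cost is a possibly lower Group #1 durability rate, and possibly a smaller per-protocol set for this endpoint.

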### 9.2 Safety endpoint analysis

All adverse events will be documented, reported, and categorized so that we may further understand the safety profile of this approach. Knowledge gained from this study will further refine consent forms and the risk benefit profile for future studies.

### 9.3 Secondary clinical efficacy endpoint analysis

Additional endpoints below will be assessed to document further the effectiveness of using the SPRINT Peripheral Nerve Stimulation (PNS) System for the symptomatic relief and management of post-amputation pain.

- Durability of the treatment effect on average pain intensity (Primary Endpoint) after 8-week home trial

The durability of the treatment effect on average pain intensity compares the proportion of subjects who successfully achieve  $\geq 50\%$  reduction from baseline in Group #1 at end of 8-week home trial relative to that in Group #2 at end of 4-week sham period, examining the statistical superiority of the proportion of successes of Group #1 over the proportion of successes of Group #2. The post-amputation pain intensity scores will be determined for each subject by applying the same method used for the primary endpoint: taking the mean of the daily average pain intensity (BPI-SF Question #5) reported in the 7-day diary at baseline compared to the mean score for the same region(s) of pain reported over the 8 weeks of treatment (*i.e.*, the average of all scores in the diaries during this period) for Group #1. To be

considered a success, subjects must have  $\geq 50\%$  reduction in all qualifying regions of pain, defined as regions of RLP and PLP with a baseline pain score  $\geq 4$  that received blinded treatment. The proportion of successes in Group #1 will be compared to the proportion of successes in Group #2 during the sham stimulation phase (Weeks 1-4 of the home trial). The null hypothesis is that there is no difference in success rates between the two treatment groups, versus the alternative hypothesis, that the success rates differ from one another.

- Durability of the treatment effect on average pain intensity (Primary Endpoint) at monthly intervals after start of therapy (3 - 12 months after start)

The analysis of the durability of the treatment effect on average pain intensity compares the proportion of subjects who successfully achieve  $\geq 30\%$  reduction from baseline in Group #1 relative to that in Group #2, examining the statistical superiority of the proportion of successes of Group #1 over the proportion of successes of Group #2. The average post-amputation pain intensity scores will be determined for each subject using BPI-SF Question #5 with 1 week recall. For Group #1, the scores reported at Visit 2 (prior to lead placement) will be compared to the score for the same region(s) of pain at each monthly interval after the end of the 8-week home trial (i.e., during the monthly follow-up calls/visits from months 3-12 after start of therapy). For Group #2, the scores reported at Visit 2 (prior to lead placement) will be compared to the score for the same region(s) of pain during the final week of the 4-week sham period. To be considered a success, subjects must have clinically-significant reduction ( $\geq 30\%$ ) from baseline in all qualifying regions of pain, defined as regions of RLP and PLP with a baseline pain score  $\geq 4$  that received blinded treatment. The proportion of successes in Group #1 at each monthly visit will be compared to the proportion of successes in Group #2 at the end of the sham period. For each month, the null hypothesis is that there is no difference in success rates between the two treatment groups, versus the alternative hypothesis, that the success rates differ from one another. Testing will be conducted at the 0.05 level of significance.

- Pain interference (BPI-SF Question #9) at monthly intervals after start of therapy

The analysis of the treatment effect on pain interference compares the proportion of subjects who successfully achieve  $\geq 50\%$  reduction in average pain interference score in Group #1 relative to that in Group #2, examining the statistical superiority of the proportion of successes of Group #1 to that of Group #2. In Group #1, the baseline average pain interference score (BPI-SF Question #9) will be compared to the average pain interference score for the same region(s) at each monthly interval after start of therapy. In Group #2, the baseline average pain interference score will be compared to the score at the end of the 4-week sham period. To be considered a success, subjects must have  $\geq 50\%$  reduction in the average pain interference score of all qualifying regions of pain, defined as regions of RLP and PLP with an average baseline pain interference score  $\geq 4$  that received blinded treatment. The null hypothesis is that there is no difference in success rates between the two treatment groups (i.e., Group #1 at the monthly interval vs. Group #2 at end of sham period), versus the alternative hypothesis, that the success rates differ from one another. Testing will be conducted at the 0.05 level of significance.

- Pain disability (Pain Disability Index (PDI)) at monthly intervals after start of therapy

The analysis of treatment effect on pain disability compares the proportion of subjects who successfully achieve  $\geq 10$  point reduction in PDI scores from baseline in Group #1 relative to that of Group #2, examining the statistical superiority of the proportion of successes of Group #1 to that of Group #2. The baseline PDI score will be compared to the PDI score at end of first 4 weeks, at the end of the home trial, and at monthly intervals after end of therapy (3-12 months after start of therapy). In Group #1, the baseline PDI score will be compared to the PDI score at each monthly interval after start of therapy. In Group #2, the baseline PDI score will be compared to the score at the end of the 4-week sham period. To be considered a success, subjects must have a  $\geq 10$  point reduction in PDI. The null hypothesis is that there is no difference in success rates between the two treatment groups (*i.e.*, Group #1 at the monthly interval vs. Group #2 at end of sham period), versus the alternative hypothesis, that the success rates differ from one another. Testing will be conducted at the 0.05 level of significance.

- Depression (Beck Depression Inventory (BDI-II)) at monthly intervals after start of therapy

The analysis of treatment effect on depression examines the statistical superiority of the mean percent improvement from baseline at monthly intervals of Group #1 relative to that of Group #2. In Group #1, the baseline BDI-II score (assessed at Visit 1) will be compared to the BDI-II score at each monthly interval after start of therapy. In Group #2, the baseline BDI-II score will be compared to the score at the end of the 4-week sham period. The null hypothesis is that there is no difference in mean percent improvement between the two treatment groups (*i.e.*, Group #1 at the monthly interval vs. Group #2 at end of sham period), versus the alternative hypothesis, that the mean percent improvements differ from one another. Testing will be conducted at the 0.05 level of significance.

- Analgesic usage

The analysis of treatment effect on analgesic usage will evaluate the change in opioid analgesic usage separately from the change in non-opioid analgesic usage (see Exploratory Measures, Section 9.4).

Changes in opioid analgesic usage will be calculated using morphine equivalent dosing (MED) to compare the mean percent change from baseline to the end of first 4 weeks in Group #1 relative to that of Group #2. Analysis will be conducted to determine if the mean change of Group #1 is statistically significantly greater than the mean improvement of the Group #2. The change in the opioid analgesic usage will be determined for subjects (who are receiving prescribed opioid medications at baseline) by taking the mean of the daily MED for the entries reported in the 7-day diary at baseline compared to the mean of the daily MED for the entries reported in the 7-day diary during the week before Visit 7 (*i.e.*, week 4 of home trial). The null hypothesis is that the mean change in MED is not significantly different in both groups, and the alternative hypothesis is that the mean change for the two groups differ.

The change in MED at the end of the 8-week home trial will also be calculated. For Group #1, the change in the opioid analgesic usage will be determined for subjects (who are receiving prescribed opioid medications at baseline) by taking the mean of the daily MED for the entries reported in the 7-day diary at baseline compared to the mean of the daily MED for the entries reported in the 7-day diary during the week before Visit 11 (*i.e.*, week 8 of home trial). This will be compared to the mean change in MED during week 4 of the home trial in Group #2 (*i.e.*, final week of the sham period), as calculated in the

previous analysis. The null hypothesis is that the mean change in MED is not significantly different in both groups, and the alternative hypothesis is that the mean change for the two groups differ.

- Prosthetic usage (hours of daily prosthetic usage recorded in diary) at end of first 4 weeks and after 8-week home trial
- The analysis of treatment effect on the prosthetic usage compares the mean rank scores (of 25 possible ranks, ranging from 0 to 24 hours) at baseline to the end of first 4 weeks and after the 8-week home trial of Group #1 relative to that of Group #2, examining the statistical superiority of the mean rank scores of Group #1 over that of Group #2. The mean rank scores will be determined for each subject by taking the 7-day mean of the daily hours of prosthetic usage reported in the 7-day diary at baseline (for the residual limb with the region of pain being used for primary efficacy) compared to the 7-day mean of the daily hours of prosthetic usage reported in the diary during the week before Visit 7 and the last week of stimulation before the end of the 8-week home trial. The null hypothesis is that the mean rank scores for both groups are not significantly different. The alternative hypothesis is that the mean ranks scores for the two groups differ.
- Subject Satisfaction Survey  
A survey will be administered to the subjects at EOT to assess their satisfaction with the study and device.

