#### 9.4 Exploratory endpoint analysis

Exploratory endpoints will be analyzed to provide information on additional outcome measures and how the system and subject characteristics affect the outcome of the investigative treatment on post-amputation pain. For all endpoints, data will be collected as described in the Schedule of Procedures (Appendix A).

- Treatment effect in Group #2  
Group #2 will receive stimulation during the second half of the home trial (Weeks 5-8), and the proportion of successes and/or mean improvements in outcome measures during this phase will be compared to those during the sham stimulation phase. In addition, a repeated measures analysis may be conducted to determine the within-subjects improvement from sham to stimulation.

Global impression of change (Patient Global Impression of Change (PGIC))

Analyses of changes in average RLP

[REDACTED]

Analyses of changes in average PLP [REDACTED]

Analyses of changes in worst RLP [REDACTED]

Analyses of changes in worst PLP [REDACTED]

[REDACTED]

- Non-opioid medication usage

[REDACTED]

- Pain Catastrophizing Scale (PCS)

[REDACTED]

- Clinician Satisfaction Survey

[REDACTED]

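### The 8-week pain durability score averages in weeks 1–4, and most secondary tests after week 4 set Group #1 against Group #2's earlier sham value, so neither can show lasting superiority to sham

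*Combined protocol and SAP*

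**What the plan says.** All of this is in Section 9.3 unless stated otherwise.

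- **8-week pain.** Success proportions are compared "in Group #1 at end of 8-week home trial relative to that in Group #2 at end of 4-week sham period". The scoring rule then takes each Group #1 subject's baseline diary mean "compared to the mean score for the same region(s) of pain reported over the 8 weeks of treatment", using every diary score in that span. Group #2 is scored on sham weeks 1–4.
- **Pain at months 3–12.** "The proportion of successes in Group #1 at each monthly visit will be compared to the proportion of successes in Group #2" as measured at the end of the sham period.
- **Pain interference (BPI-SF Question 9) and PDI.** The null hypotheses are written as "Group #1 at the monthly interval vs. Group #2 at end of sham period".
- **Depression.** Group #1 is assessed monthly. "In Group #2, the baseline BDI-II score will be compared to the score at the end of the 4-week sham period".
- **8-week opioid MED.** Group #1's change is taken from the week-8 diary. "This will be compared to the mean change in MED during week 4 of the home trial in Group #2".
- **8-week prosthetic use.** The last week of stimulation is used; the Group #2 comparison period is not named.

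Pain, interference, PDI and BDI-II are framed as superiority comparisons, and MED as a between-group difference. A 0.05 level is stated for months 3–12 pain, interference, PDI and BDI-II. Section 9.4 has Group #2 on stimulation in weeks 5–8, and Section 7.5.11 removes leads at week 8. The visible text gives no adjustment for time and no caveat about the comparator.

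**The concern.** There are two separate problems.

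**(a) The score.** A durability endpoint should show whether relief present early is still present late. Section 9.1 already averages weeks 1–4 for the primary endpoint, and the 8-week score uses those same diary days again as half of its data. The rule is clear and can be programmed, so this is not an ambiguous endpoint. It answers a different question from its label, and partly re-tests the primary period. It overstates durability if relief fades and understates it if relief builds.

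**(b) The comparator.** Section 9.1 attributes a group difference to the device because the groups differ only in active or sham stimulation during the first 4 weeks. That argument holds only while the sham arm is on sham. After week 4 there is no concurrent sham, so the tests set one group at a later time against the other at an earlier time. For months 3–12 the values also differ in device status, because the leads are out. Randomization balances neither time nor device status. A significant or null result cannot be separated from regression to the mean, waning placebo response or natural change. At stake is a claim of superiority to sham at week 8, or as late as month 12, that the design cannot support.

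**Working it through.** No figure in the plan is in dispute. The sample size (up to 54, 27 per group, Section 6.2) enters only as an input. The documents give no fade, SD, correlation, drift, later response or number of opioid users, so every such input below is an assumption.

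**(a) Arithmetic of the 8-week mean.** With complete diaries and percentage reductions r1 (weeks 1–4) and r2 (weeks 5–8), the 8-week reduction is (r1 + r2)/2. Success at 50% needs only r2 ≥ 100 − r1.

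| r1 | r2 | 8-week mean | 8-week rule | Weeks 5–8 rule |
|---|---|---|---|---|
| 70 | 30 | 50 | success | failure |
| 75 | 25 | 50 | success | failure |
| 100 | 0 | 50 | success | failure |
| 20 | 70 | 45 | failure | success |

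**Success rates.** Take r1 and r2 as bivariate normal, SD 25 points each, correlation 0.7, one qualifying region. The SD of the 8-week mean is 25 × √((1 + 0.7)/2) = 23.05.

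- No change (means 60 then 60): Φ(10/23.05) = 66.8% on the 8-week mean; Φ(10/25) = 65.5% on weeks 5–8.
- Fade (60 then 40): Φ(0) = 50.0%; Φ(−10/25) = 34.5%.
- Build (40 then 60): Φ(0) = 50.0%; Φ(10/25) = 65.5%.

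Misclassification, and the case of two regions that must both pass (between-region correlation 0.6, range 0.3–0.9), come from 2,000,000 simulated subjects per setting:

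| Scenario | 8-week successes failing weeks 5–8 | Weeks 5–8 successes missed | Two regions: 8-week mean | Two regions: weeks 5–8 |
|---|---|---|---|---|
| No change | 9.6% | 7.9% | 53% (49–60) | 52% (47–59) |
| Fade | 33.6% | 3.7% | 35% (30–43) | 21% (16–28) |
| Build | 2.6% | 25.7% | 35% (30–43) | 52% (47–59) |

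For SD 20 to 35 in one region, the weeks 5–8 rate is 31–39% under fade and 69–61% under build, against 50% on the 8-week mean throughout.

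**(b) Success proportions.** Suppose the device has no effect and response changes only with time. For 27 per arm, sum the binomial probabilities of all pairs (x1, x2) that reject at two-sided 0.05. The visible text names no test here. Pearson chi-square is assumed, z = ((x1 − x2)/27) / √(2p̄(1 − p̄)/27), with Fisher's exact test as a check. Week-4 sham response is 30%.

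| Later Group #1 response | False superiority, chi-square | Wrongly favours sham, chi-square | False superiority, Fisher | Wrongly favours sham, Fisher |
|---|---|---|---|---|
| 30% | 2.7% | 2.7% (symmetry) | 1.3% | 1.3% (symmetry) |
| 40% | 11.8% | – | 7.2% | – |
| 20% | 0.3% | 14.3% | 0.1% | 7.4% |

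For week-4 response of 20–40% (chi-square), false superiority is 2.3–2.9% with no drift and 9.9–14.3% at +10 points. At −10 points it is 0.2–0.3%, with 11.8–18.6% wrongly favouring sham.

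These figures describe a wholly later Group #1 value. They fit the monthly endpoints, not the 8-week pain test as written, which is half concurrent with sham.

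**Ten monthly pain tests (months 3–12) sharing one Group #2 value.** With latent correlation 0.3–0.9 between months and 60,000 replicates, the chance of at least one false superiority is 7–13% with no drift, 24–37% if later response is 40%, and 1–2% if it is 20% (31–48% for at least one result favouring sham). The no-drift figure is multiplicity, not confounding.

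**8-week MED.** Two-sample t-test, noncentrality δ√(n/2), with n = 8, 14, 20 opioid users per arm. False significance in the direction of drift is 6.8%, 9.3%, 11.7% for δ = 0.25 SD and 15.2%, 24.6%, 33.8% for δ = 0.5 SD, against 2.5% with no drift. It is symmetric for opposite drift.

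**The case against.** The 8-week score deliberately carries the primary endpoint's averaging method over a longer period. A treatment-period average is a coherent quantity and less noisy than a single week. The plan is not blind to fading either: months 3–12 pain uses a one-week recall, and MED and prosthetic use take late diary windows. On that view only the label is at fault. For the comparator, the crossover leaves no later sham, the plan states openly what it compares, and a caveat might be enough. Because the 8-week mean overlaps the sham period, drift is also diluted in that test, and moving the window to weeks 5–8 removes that overlap. The sizes rest wholly on assumptions, and with no change or drift they are small. These are secondary endpoints of a pilot.

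Much of this is accurate, and it limits the weight of the point. It does not remove it. The average is legitimate as a supportive summary, but it cannot answer whether relief lasted to week 8, and the later windows used elsewhere show that a direct measure is available. The crossover explains why there is no control; it does not require a superiority test without one. Disclosing the comparator does not make the test interpretable. The loss of overlap does no harm if formal testing of that endpoint is dropped as well.

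**Conclusion.** The concern holds on both parts, as a should-fix matter for secondary endpoints. What the plan scores and compares is read directly from visible text. The sizes are illustrations of what could happen.

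- **(a)** The 8-week result need not reflect weeks 5–8. In the assumed one-region scenarios the two success rates differ by about 15 points in either direction (50.0% against 34.5% or 65.5%) and by 1.3 points with no change (66.8% − 65.5%).
- **(b)** Pain after week 4, monthly interference, PDI and BDI-II after week 4, and 8-week MED cannot support superiority to sham. A 10-point drift moves the false-superiority rate of a wholly later comparison from 2.7% to 11.8% or 0.3% at a 30% week-4 response. The direction of drift is unknown.

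The primary endpoint is unaffected, as are the concurrent week-4 comparisons, including week-4 MED. Prosthetic use at 8 weeks is outside the point, because its Group #2 period is not stated. Redacted text may say more on imputation and multiplicity; the conclusion does not depend on it.

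**What to change.** 1. Score Group #1's 8-week durability on the weeks 5–8 diaries, or on the week-8 diary as MED and prosthetic use already do. Keep the weeks 1–8 mean as a supportive summary, and align the wording of the endpoint in Section 9.3.
2. Confirm that the missing-diary rule extends to weeks 5–8. The visible rule in Section 9.1.5 reads "Data missing from any day of diary during the first 4 weeks of the home trial will be imputed from baseline diary data"; the text after it is redacted.
3. Report all results after week 4, including 8-week pain and 8-week MED, as Group #1 estimates with 95% CIs, labelled uncontrolled. Group #2's sham-period value may be shown as a non-concurrent descriptive reference, without superiority or difference tests. Keep the concurrent week-4 between-group tests.
4. Minor: state which Group #2 period is used for 8-week prosthetic use, or report it descriptively. If any monthly tests are kept, state a multiplicity rule unless the redacted text already does.

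The cost is plan wording and programming; the diaries and monthly scores are already scheduled. The price is giving up any formal claim of superiority to sham after week 4.
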